8.4 Withdrawal of individual subjects

Subjects can leave the study at any time for any reason if they wish to do so without any consequences. The investigator can decide to withdraw a subject from the study for urgent medical reasons.

8.4.1 Specific criteria for withdrawal (if applicable)

Not applicable

8.5 Replacement of individual subjects after withdrawal

Subjects who opt to withdraw will not be replaced.

8.6 Follow-up of subjects withdrawn from treatment

Not applicable

8.7 Premature termination of the study

A premature termination of the study is not expected. However, in case of a premature termination of the study no consequences for the study subjects are to be expected.

9 SAFETY REPORTING

9.1 Temporary halt for reasons of subject safety

In accordance to section 10, subsection 4, of the WMO, the sponsor will suspend the study if there is sufficient ground that continuation of the study will jeopardise subject health or safety. The sponsor will notify the accredited METC without undue delay of a temporary halt including the reason for such an action. The study will be suspended pending a further positive decision by the accredited METC. The investigator will take care that all subjects are kept informed.

9.2 AEs, SAEs and SUSARs

9.2.1 Adverse events (AEs)

The interventions performed in this pilot study are blood collection and a vaginal swab. Adverse events are defined as any undesirable experience occurring to a subject during the study. Events considered related to the experiment, reported spontaneously by the subject or observed by the investigator or his staff will be recorded. Regular laboratory screening is part of the standard care on the PICU, although unlikely, adverse reactions from blood collection can occur. Personnel collecting blood specimens know what can occur and how best to manage the reactions. This is an observational study, adverse drug events are not caused by study intervention. All adverse events due to blood collection, vaginal swab collection or faeces collection will be registered.

9.2.2 - Serious adverse events (SAEs)

A serious adverse event is any untoward medical occurrence or effect that

- results in death;
- is life threatening (at the time of the event);
- requires hospitalisation or prolongation of existing inpatients' hospitalisation;
- results in persistent or significant disability or incapacity;
- is a congenital anomaly or birth defect; or
- any other important medical event that did not result in any of the outcomes listed above due to medical or surgical intervention but could have been based upon appropriate judgement by the investigator.

An elective hospital admission will not be considered as a serious adverse event

In line with the CCMO guidelines, the SAEs will be reported to the MEC via yearly line listings together with the progress report.

9.2.3 Suspected unexpected serious adverse reactions (SUSARs)

Not applicable

9.3 Annual safety report

Not applicable

9.4 Follow-up of adverse events

All AEs will be followed until they have abated, or until a stable situation has been reached. Depending on the event, follow up may require additional tests or medical procedures as indicated, and/or referral to the general physician or a medical specialist. SAEs need to be reported till end of study within the Netherlands, as defined in the protocol

9.5 Data Safety Monitoring Board (DSMB) / Safety Committee

Not applicable

10 STATISTICAL ANALYSIS

10.1 Primary study parameter(s)

Statistical analyses

The statistical analyses will be conducted using the statistical software R.

Continuous variables will be expressed as mean and standard deviation for normally distributed variables, median and interquartile range for not normally distributed variables.

To analyse the association between the gut microbiome and PCOS compared to controls, reads with some level of similarity will be grouped into operational taxonomic units (OTUs). Alpha and beta diversity analyses will be calculated to estimate the abundance and diversity of species within samples.

Alpha diversity comparisons will be analysed with Shannon diversity index and richness as continuous variables. Higher Shannon diversity index is associated with a more diverse and rich vaginal microbiome. It measures the number of species and the differences between species abundances. A logistic regression model will be used to test the changes of alpha diversity in PCOS and non-PCOS women. Same analyses will be conducted for changes of alpha diversity in overweight/obese and lean women with or without PCOS. Linear regression analyses will be conducted to study the correlation between the diversity of the microbiome (Alpha and Beta diversity) and parameters such as hyperandrogenism, rated as serum total testosterone level or Free Androgen Index (FAI). Other PCOS-associated variables included in the univariable linear regression analyses are: hirsutism, acne, BMI, LH/FSH, testosterone, androstenedione. Significant variables from the univariable regression analyses will be tested in a multivariable linear regression model. To correct for multiple testing, Bonferroni's correction will be conducted.

UniFrac will be used to compare the (dis-)similarities among the microbial communities samples (beta-diversity). Unweighted UniFrac analyses is based on presence/absence of difference taxa and abundances and weighted UniFrac will take the abundances of different taxa into consideration. The results from Unifrac analyses will be represented using Principal Coordinate Analysis (PCoA) plots. PCoA plots will represent the dissimilarity of microbiome samples. The PCoA will be based on the overall structure of the gut microbiome in all samples for PCOS and controls.

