Various factors have been reported to contribute to the pathophysiology of PCOS, but due to the heterogeneity of the syndrome, the pathophysiology remains unclear. However, studies emerged on the crucial role of the gut microbiome in human health. Recent studies confirmed that the gut microbiome is altered in women with PCOS compared to healthy women (4-7), and some of these alterations have been linked to the clinical markers of PCOS (4, 5). Different PCOS phenotypes may show different gut microbiome features due to the heterogeneity of this syndrome, which makes it hard to detect the significant changes in the gut microbiome. Age, obesity, androgen status, and insulin resistance or glucose intolerance should all be taken into account while studying the gut microbiome of PCOS patients.

Even though studies have proven that PCOS patients have an altered gut microbiome, the characteristics of microbiome diversity and the specific types of gut bacteria have remained inconsistent. Studies reported on specific alterations of alpha and beta diversity in PCOS patients. Although some studies have shown that decreased alpha diversity and altered beta diversity were associated with PCOS (4, 5, 8), many studies have reported that microbial diversity remained unchanged (9-11).

Studies have investigated correlations between the clinical features of PCOS and the gut microbiome. Features of PCOS such as hyperandrogenism, hirsutism, insulin resistance, and obesity can all have an impact on the gut microbiome to some extent. The decrease in α -diversity has been linked to total testosterone levels and hirsutism (9, 12), and changes in β -diversity were also correlated with hyperandrogenism (5). Also, some even suggested that the hyperandrogenism seen in the PCOS rodent model may affect the gut microbiome independently of diet (13). The role of metabolic factors, such as obesity and insulin resistance, in the PCOS patient's gut microbiome, remains unclear. Although another study showed that obesity itself is linked to a decrease in gut microbial diversity (12), most studies on the gut microbiome in PCOS have included BMI-matched controls to exclude the

influence of body weight. In another study, BMI was found to positively correlate with three bacterial species, while waist-to-hip ratio and fat mass were also found to significantly correlate with the levels of multiple species (9, 12).

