1. INTRODUCTION AND RATIONALE

Polycystic ovary syndrome (PCOS) is an endocrine disorder that affects up to 10% of reproductive-aged women worldwide. According to the Rotterdam criteria the syndrome is diagnosed based on two of the following three criteria (2): ovarian dysfunction (OD), hyperandrogenism (HA) (clinical or biochemical), and/or polycystic ovarian morphology (PCOM) (1). PCOS phenotypes are currently classified as phenotype-A (HA+ OD+ PCOM), phenotype-B (HA+OD), and phenotype-C (HA+PCOM). Phenotype-A or full-blown phenotype is present in half of the patients who present in the clinic. See Supplementary Table 1.

In PCOS women, not only is infertility a concern, but the syndrome is also associated with obesity, insulin resistance, type 2 diabetes mellitus, metabolic syndrome, and cardiovascular risk factors (3). Various factors have been reported to contribute to the pathophysiology of PCOS, such as lifestyle, metabolic status, and genetic and epigenetic variants. However, studies emerged on the crucial role of the gut microbiome in human health. Recent studies confirmed that the gut microbiome is altered in women with PCOS (4-6). The gut microbiome composition of PCOS patients is altered compared to healthy women and some of these alterations have been linked to the clinical markers of PCOS (4, 5). PCOS patients seem to have a leaky gut: the gut bacteria change the intestinal lining, resulting in the release of bacterial endotoxins into the bloodstream. This could activate pro-inflammatory cytokines, promoting insulin resistance, hyperandrogenism, and fat storage, all of which are linked to PCOS (16).

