10.2 Secondary study parameter(s)

To analyse the association between the vaginal microbiome and PCOS compared to controls, the bacterial taxa will be first classified to the genus level. The relative abundance will be quantified based on each taxa contribution to an individual sample. Operational taxonomic unit (OTU) abundance will be noted for all samples. Alpha and Beta diversity will be calculated. Associations between the vaginal microbiome (Alpha and Beta diversity) and PCOS-associated variables as BMI, hirsutism, acne, testosterone, androstenedione, LH/FSH, insulin, will be tested in a linear regression model.

To investigate the association between the bacterial diversity and markers for gut permeability and inflammation in PCOS patients, a logistic regression model will be used. Leaky gut markers as calprotectin, zonulin, lipopolysaccharide and soluble CD15 and inflammation markers as CRP, IL-22, IL6 and TNF-a will be tested in the logistic regression model. Also the results of the Food Frequency Questionnaire (FFQ) will be analysed in the logistic regression model.

Differences on clinical characteristics and metabolic biomarkers will be evaluated using t-test or a one-way analysis of variance (ANOVA) for normally distributed variables or non-parameter Wilcoxon test for non-normally distributed variables. Two-sided tests will be used, and p-values less than 0.05 will be considered statistically significant.

As for the metabolomic analysis, the raw data will be pre-processed first. Log-transformation and centering are techniques used to make the data normal distributed. To investigate differences between the PCOS and controls, univariate analysis will be performed to examine each metabolite feature separately.

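### The main PCOS v non-PCOS gut alpha-diversity model in Section 10.1 names no covariate: age is in no Section 10 model, gut-model BMI is only a screened term in separate linear models, and the FFQ's model is unclear

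*Protocol*

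**What the plan says.** Section 10.1 gives the main gut alpha-diversity comparison one sentence: "A logistic regression model will be used to test the changes of alpha diversity in PCOS and non-PCOS women". The next sentence extends it to the BMI groups: "Same analyses will be conducted for changes of alpha diversity in overweight/obese and lean women with or without PCOS". Neither names a covariate.

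The section then turns to linear regressions of diversity on features of PCOS. BMI is one of the candidates: "Other PCOS-associated variables included in the univariable linear regression analyses are: hirsutism, acne, BMI, LH/FSH, testosterone, androstenedione". A selection rule follows: "Significant variables from the univariable regression analyses will be tested in a multivariable linear regression model". PCOS status is not listed in these linear models. The linear model for the vaginal microbiome in Section 10.2 also lists BMI, with no screen stated.

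For diet, Section 10.2 says: "Also the results of the Food Frequency Questionnaire (FFQ) will be analysed in the logistic regression model". The logistic model just described there concerns "markers for gut permeability and inflammation in PCOS patients, a logistic regression model will be used". No binary outcome is given for it.

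On background, the Rationale in the Summary says: "Age, obesity, androgen status, and insulin resistance or glucose intolerance should all be taken into account while studying the gut microbiome of PCOS patients". Section 3 calls diet a strong correlate of the gut microbiome and gives this as the reason for recruiting from one region. Section 3 also sets four cells of 50 women (PCOS or control, overweight/obese or lean). Sections 4.2 and 4.3 set an age range of 18 to 45 for both groups and state no age matching. Section 12.1 lists age and BMI among the data extracted, and Section 8.3 plans the FFQ.

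**The concern.** This is a non-randomised comparison. Cases come from a reproductive medicine clinic, and controls come from that clinic and from online advertisement (Section 11.2). The two groups may differ in age, in diet, and in BMI within the open-ended overweight/obese category. If such a variable also relates to gut diversity, an unadjusted logistic model attributes its effect to PCOS, or lets it hide a real difference.

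The protocol recognises these variables and collects them. Yet Section 10 assigns BMI and the FFQ to other models and age to none. The univariable screen is also a poor way to choose confounders: a variable can bias the group comparison without reaching significance on its own.

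**Working it through.** **Which variable enters which model**

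- PCOS v non-PCOS, gut alpha diversity (10.1, logistic): no covariate named.
- Diversity on PCOS features, gut (10.1, linear): BMI is a candidate and goes forward only if univariably significant; age, diet and PCOS status are not listed.
- Vaginal microbiome on PCOS features (10.2, linear): BMI listed with no screen stated; age and diet not listed.
- Permeability and inflammation markers in PCOS patients (10.2, logistic): the FFQ on the nearest reading; outcome not stated.

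**What the design already controls**

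The 50/50/50/50 quotas balance BMI category. The age limits and regional restriction narrow age and diet. What can still differ is age within 18 to 45, diet within the region, and BMI within category.

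**How large the effect could be**

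The sample size in Section 4.4 comes with no power, effect size or SD, so there is no planned figure to reproduce. The inputs from the protocol are 100 v 100 and a two-sided 5% level (stated in 10.2). The covariate gap D (in SD) and its correlation r with Shannon diversity are assumptions.

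With no true PCOS effect, the spurious shift is D × r SD, and the noncentrality of the two-sample t test is D × r × √(100/2) = 7.07 × D × r.

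- D 0.3, r 0.1: shift 0.03, noncentrality 0.21, false-positive rate 5.5%.
- D 0.3, r 0.2: shift 0.06, noncentrality 0.42, rate 7.1%.
- D 0.5, r 0.2: shift 0.10, noncentrality 0.71, rate 10.8%.
- D 0.5, r 0.3: shift 0.15, noncentrality 1.06, rate 18.4%.

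For scale, 100 v 100 detects about 0.40 SD with 80% power.

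Simulating the logistic test itself (5,000 runs per setting, Monte Carlo error about 0.3 points) gives:

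- Balanced covariates: 5.3% unadjusted; 5.2 to 5.5% adjusted.
- Age, D 0.5, r 0.2: 10.8% unadjusted; 5.1% with age and BMI group in the model.
- BMI, with PCOS women 4 units heavier in the overweight cell only, at 0.05 SD per unit: 0.20 SD in half the sample, so 0.10 SD overall. The rate is 10.5% unadjusted, 10.5% with age and BMI group, and 5.6% once continuous BMI is added. At 2 units and 0.02 SD per unit there is no inflation (5.3%).
- Diet, D 0.5, r 0.3: 18.0% unadjusted. Adding the FFQ gives 5.2%, 6.6%, 8.3% and 11.5% at FFQ reliability 1.0, 0.7, 0.5 and 0.3.

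**If Bonferroni applies**

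Section 10.1 mentions Bonferroni without fixing its scope. If it covers the two alpha-diversity measures (Shannon and richness), the level is 2.5%. Shifts of 0.06 and 0.15 SD then give 3.8% and 11.8%. The absolute rates fall, but the inflation relative to 2.5% remains.

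**The screen**

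By Fisher's z at n = 200, the statistic has mean atanh(r) × √197, which is 1.41 at r = 0.1 and 2.85 at r = 0.2. The chance of passing a 5% screen is therefore 29% and 81%. A covariate strong enough to matter can be dropped.

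**The case against.** The strongest reply is that a covariate list is commonly left to an analysis plan, and that silence in one sentence is not a decision against adjustment. That is partly right. Section 10.1 calls the linear regressions univariable but does not say so of the logistic model, and nothing bars adjustment. A reader might infer that the protocol prescribes an unadjusted analysis; it does not go that far. What stands is that Section 10 already names the model type, allots BMI and the FFQ to other models and sets a selection rule, and it leaves age out throughout.

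Four further limits hold:

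- A reader might infer that BMI is uncontrolled, or only ever screened. The quotas balance BMI category, and the vaginal model in 10.2 lists BMI without a screen.
- A reader might take the Rationale sentence on age and obesity as a confounder list that Section 10 contradicts. It follows a remark on phenotype heterogeneity, concerns PCOS patients, and also names androgen status and insulin resistance. It shows that the variables are thought relevant, and no more.
- The BMI-group sentence may mean PCOS v control within a BMI group, or overweight/obese v lean. No figure for a 50 v 50 comparison should be built on it. On either reading it does not adjust for BMI within category.
- Every covariate gap and correlation above is assumed, and the low ends show no harm.

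**Conclusion.** The point holds as an improvement that should be made before analysis. As written, the main case-control comparison names no adjustment, and age, diet and BMI within category are left open to confound it.

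The documents do not show that the result will be biased. A reader might infer that an error rate of 11 to 18% is to be expected; that range needs a covariate gap of 0.5 SD and a correlation of 0.2 to 0.3 with Shannon diversity, and the protocol gives neither. Under those assumptions, an accurately measured covariate in the model brings the rate back to about 5%. A covariate measured with error, as the FFQ is likely to be, helps but leaves some bias. With small or no imbalance the nominal level holds.

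**What to change.** In Section 10.1:

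- Enter age and BMI (as a continuous value) in the PCOS v non-PCOS model, whatever their univariable significance.
- Say that the univariable screen is not used to choose confounders for this comparison.
- Report beside it the version with age and BMI group only. BMI may lie on the pathway, since the Introduction describes gut changes as "promoting insulin resistance, hyperandrogenism, and fat storage, all of which are linked to PCOS".
- Do not add androgen status, which is part of the case definition (Supplementary I), or insulin resistance, which the same passage places downstream.

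In Section 10.2:

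- State which model the FFQ enters and what its outcome is.
- Use one FFQ summary, named in advance, as a sensitivity adjustment of the case-control model where both cases and controls have FFQ data, and note residual confounding from FFQ error. Section 8.3 asks patients for the FFQ and covers controls only by saying that they follow the study protocol, so confirm that controls complete it.

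The cost is a few degrees of freedom and some wording; age, BMI and the FFQ are already planned. With balanced covariates, simulated power at 0.4 SD is 79% with or without the added terms. If 10 to 20% of women lacked FFQ data (assumed), the sensitivity model's detectable difference would move from 0.40 to 0.42–0.45 SD.

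The real downside is interpretive. If 0.1 of a 0.4 SD difference acts through BMI, the model with continuous BMI returns 0.30 SD (power 50%), against 0.40 SD (78%) with age and BMI group only. Hence both should be shown.

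The BMI cut-offs in Sections 4.1 (above 25; 18 to 25) and 4.4 (above 30; 19 to 25) conflict. That is a separate point, but they must be reconciled before BMI group can be coded.

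### Sections 10.1 and 10.2 plan linear regression of beta diversity, but the named measure, UniFrac, has one value per pair of samples and no per-woman score is defined.

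*Protocol*

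**What the plan says.** Protocol 10.1 commits to a model for both kinds of diversity: "Linear regression analyses will be conducted to study the correlation between the diversity of the microbiome (Alpha and Beta diversity"), related to hyperandrogenism measured as serum total testosterone or Free Androgen Index (FAI). The list then continues: "Other PCOS-associated variables included in the univariable linear regression analyses are: hirsutism, acne, BMI, LH/FSH, testosterone, androstenedione". Two further steps build on these regressions: "Significant variables from the univariable regression analyses will be tested in a multivariable linear regression model", and "To correct for multiple testing, Bonferroni's correction will be conducted".

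For alpha diversity, 10.1 names the outcomes: Shannon index and richness, both continuous. For beta diversity it names a distance: "UniFrac will be used to compare the (dis-)similarities among the microbial communities samples (beta-diversity"), in an unweighted and a weighted version. Section 8.1.3 says the same in a text that covers gut and vaginal samples. The ordination is introduced for display: "The results from Unifrac analyses will be represented using Principal Coordinate Analysis (PCoA) plots", and "The PCoA will be based on the overall structure of the gut microbiome in all samples for PCOS and controls".

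Section 10.2 repeats the regression plan for the second site: "Associations between the vaginal microbiome (Alpha and Beta diversity) and PCOS-associated variables", now including insulin, are to be tested by linear regression.

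The Summary makes beta diversity part of the main study parameter. Section 8.1.1 extends the main endpoint to diagnostic and metabolic characteristics.

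**The concern.** A linear regression needs one outcome value for each row of explanatory variables. Here the rows are women, each with one testosterone value, one BMI and so on. UniFrac does not give a value for a woman; it gives a dissimilarity between two women's samples. The plan names the model and the distance, but not the step that turns one into an outcome for the other.

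That step matters. A PCoA axis score says where a woman lies along one main direction of variation. Her distance to the centroid says how atypical she is, whatever the direction. Two women at opposite ends of an axis can have the same distance to the centroid, so a hormone that shifts the community along that axis may show in one score and not in the other.

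The choice also feeds into two things that 10.1 promises: how many tests the Bonferroni correction divides by, and which variables count as significant and enter the multivariable model. Because these regressions serve the main endpoint, the outcome should not be left to be chosen once the data are in hand.

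**Working it through.** The protocol gives no figure for this point that could be reproduced, so the check sets the model beside the measure and then counts.

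**1. Unit of each quantity**
- Explanatory variables (10.1 and 10.2): one value per woman.
- Shannon index and richness (10.1): one value per woman. Linear regression fits.
- UniFrac (8.1.3 and 10.1): one value per pair of samples, in two versions. Linear regression on per-woman variables does not fit without a further definition.
- PCoA (10.1): gives coordinates per woman, but is described only as a plot. No axis, number of axes or choice of UniFrac version is named as an outcome.

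**2. Size of the mismatch**
- Women: 100 with PCOS and 100 controls (4.4), so n = 200.
- Pairs: n(n − 1)/2 = 200 × 199/2 = 19,900 values per UniFrac version, against 200 values of each explanatory variable.

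**3. Number of univariable gut tests in 10.1**

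Number of variables, v:
- Hirsutism, acne, BMI, LH/FSH, testosterone and androstenedione make 6.
- FAI is a seventh if it is used. The text offers total testosterone or FAI and then lists testosterone again, so v is 6 or 7. LH/FSH is counted as one variable.

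With k beta outcomes per UniFrac matrix and two matrices:
- Alpha tests = v × 2 = 12 or 14.
- Beta tests = v × 2 × k.
- Total = 2v(1 + k).

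| Beta outcomes per matrix | v = 6 | v = 7 | Bonferroni level at 0.05 |
|---|---|---|---|
| k = 1 | 12 + 12 = 24 | 14 + 14 = 28 | 0.05/24 = 0.0021; 0.05/28 = 0.0018 |
| k = 3 (for example axes 1 to 3) | 12 + 36 = 48 | 14 + 42 = 56 | 0.05/48 = 0.0010; 0.05/56 = 0.0009 |

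The 0.05 is the two-sided level stated in 10.2. The table assumes that all univariable gut regressions form one Bonferroni family, which the protocol does not say. For either v, going from one to three outcomes per matrix doubles the denominator.

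**The case against.** The strongest reply is that PCoA supplies the missing score. Its axis coordinates are per-woman values, regressing them on covariates is a routine reading, and dbRDA is itself linear regression on principal coordinates. On this view the protocol has fixed the distance, the ordination and the model class, and only the choice of axes remains, which an analysis plan not shown here could supply. Much of this stands. A reader might infer that the regression cannot be run at all; the text does not support that, because a feasible reading exists. What remains is that the protocol does not leave the method open. It names linear regression at both sites, for a measure that does not fit it as written, and gives PCoA no role beyond plots.

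Three other strong readings also fail:
- **Pairs as independent rows.** A reader might infer that the 19,900 pairs will be entered in this way. That would be invalid, but nothing in the protocol says it will be done.
- **No PCoA for vaginal data.** One sentence ties the PCoA to the gut, but another in 10.1 speaks of microbiome samples in general, 8.1.3 covers both sites, and the site wording in 10.1 is loose elsewhere too.
- **No formal beta-diversity test of PCOS against controls.** The protocol names none, but that is an omission which a separate analysis plan may fill.

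It is also fair to say that the Bonferroni denominator is unstated for alpha diversity as well, so beta diversity is only part of that uncertainty.

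**Conclusion.** The point holds as a mismatch between the stated model and the stated measure. Sections 10.1 and 10.2 regress beta diversity on per-woman variables, the only named measure is pairwise, and no per-woman outcome is defined. It should be fixed before analysis because beta diversity is part of the main parameter.

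The mismatch itself rests on the text alone. The consequence for multiplicity depends on assumptions: 24 to 28 tests with one outcome per matrix or 48 to 56 with three axes each, given one Bonferroni family, two alpha outcomes, both UniFrac versions and six or seven variables. The protocol gives no basis for putting a figure on lost power or false-positive risk in this study, and none is claimed.

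**What to change.** In 10.1 and 10.2, replace linear regression of beta diversity with a distance-based permutation model (PERMANOVA or dbRDA) on each UniFrac matrix. Specify one test per variable per matrix and count these tests in the Bonferroni denominator. Keep linear regression for Shannon index and richness, and keep the PCoA plots as display. The number of permutations must let p-values fall well below the corrected level; 9,999, for instance, allows a smallest p-value of 1/10,000 = 0.0001.

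If linear regression of beta diversity is preferred, state in advance, for gut and for vaginal data, which PCoA axes of which UniFrac matrix are the outcomes, and count each axis in the denominator.

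Either way, say whether total testosterone, FAI or both are used and which tests form the Bonferroni family, so that the denominator is a fixed number. The cost is a few sentences of protocol text and a few lines of R, with no extra samples, data or participants.
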